8.2 ASSESSMENT OF SAFETY EVENTS

AE information collected will include event description, date of onset, assessment of severity and relationship to study product and alternate etiology (if not related to study product), date of resolution of the event, seriousness and outcome. The assessment of severity and relationship to the study product will be done only by those with the training and authority to make a diagnosis and listed on the Form FDA 1572 as the site principal investigator or sub-investigator. AEs occurring during the collection and reporting period will be documented appropriately regardless of relationship. AEs will be followed through resolution.

SAE's will be:

• Assessed for severity and relationship to study product and alternate etiology (if not related to study product) by a licensed study physician listed on the Form FDA 1572 as the site principal investigator or sub-investigator.

Version Date: 09/14/2021

• Recorded on the appropriate SAE report form, the medical record and captured in the clinical database.

• Followed through resolution by a licensed study physician listed on the Form FDA 1572 as the site principal investigator or sub-investigator.

For timeframe of recording adverse events, please refer to section **6.1**. All serious adverse events recorded from the time of first investigational product administration must be reported to the sponsor with the exception of any listed in section **8.4**.

8.3 REPORTING OF SERIOUS ADVERSE EVENTS

Any AE that meets protocol-defined serious criteria or meets the definition of Adverse Event of Special Interest that require expedited reporting must be submitted immediately (within 24 hours of awareness) to OSRO Safety using the CCR SAE report form. Any exceptions to the expedited reporting requirements are found in section **8.4**.

All SAE reporting must include the elements described in section 8.2.

SAE reports will be submitted to the Center for Cancer Research (CCR) at: [contact] and to the CCR PI and study coordinator. CCR SAE report form and instructions can be found at:

https://ccrod.cancer.gov/confluence/display/CCRCRO/Forms+and+Instructions

Following the assessment of the SAE by OSRO, other supporting documentation of the event may be requested by the OSRO Safety and should be provided as soon as possible.

8.4 WAIVER OF EXPEDITED REPORTING TO CCR

As death due to disease progression is part of the study objectives, and captured as an endpoint in this study, it will not be reported in expedited manner to the sponsor. However, if there is evidence suggesting a causal relationship between the study drug and the event, report the event in an expedited manner according to section **8.3**.

8.5 SAFETY/OTHER REPORTING CRITERIA TO THE PHARMACEUTICAL MANUFACTURER (CTEP)

The NCI Cancer Therapy Evaluation Program (CTEP) is providing clinical grade recombinant human IL-15 for this study. Because the CTEP is responsible for the Clinical Material and Confidential Information which it develops, CTEP must ensure that the Clinical Material and Confidential Information are used, communicated and reproduced appropriately and completely. The PI agrees to use the Clinical Material in accordance with all Federal laws and regulations that govern the use of investigational agents in clinical trials.

The following will be provided to CTEP during the course of the clinical study:

- 1. Initial FDA submission/approval, including: FDA-submitted protocol document; any FDA comments regarding the protocol and IND submission, including correspondence regarding the IND submission safe-to-proceed notice; and, a copy of the FDA acknowledgement of the IND submission(s) stating the IND number, sponsor, title and date of submission.
- 2. Documentation of initial IRB approval of the FDA-submitted protocol document and annual continuing IRB review approvals.
- 3. All significant protocol amendments, including changes in study size, eligibility criteria, study design and end points.

Version Date: 09/14/2021

4. Notification of any changes in protocol status or other significant events related to the Protocol.

- 5. Notification of any changes in IND status.
- 6. Copies of any FDA communications.
- 7. Copies of IND Annual Reports.
- 8. All IND Safety Reports submitted to the FDA per 21 CFR 312.32. Copies of all IND Safety Reports submitted to the FDA should be forwarded electronically to [contact] (please provide protocol number in subject line).
- 9. Any abstracts, manuscripts, and publications.

Additional safety and efficacy data may also be requested by CTEP to facilitate the development of the Clinical Material across CTEP supported trials.

8.6 REPORTING PREGNANCY

All required pregnancy reports/follow-up to OSRO will be submitted to: [contact] and to the CCR PI and study coordinator. Forms and instructions can be found here: https://ccrod.cancer.gov/confluence/display/CCRCRO/Forms+and+Instructions

8.6.1 Maternal exposure

If a patient becomes pregnant during the course of the study, the study treatment should be discontinued immediately and the pregnancy reported to the Sponsor no later than 24 hours of when the Investigator becomes aware of it. The Investigator should notify the Sponsor no later than 24 hours of when the outcome of the Pregnancy becomes known.

Pregnancy itself is not regarded as an SAE. However, congenital abnormalities or birth defects and spontaneous miscarriages that meet serious criteria (section **8.1.2**) should be reported as SAEs.

The outcome of all pregnancies (spontaneous miscarriage, elective termination, ectopic pregnancy, normal birth, or congenital abnormality) should be followed up and documented.

8.6.2 Paternal exposure

Male patients should refrain from fathering a child or donating sperm during the study and for 90 days after the last dose of study drug.

Pregnancy of the patient's partner is not considered to be an AE. However, the outcome of all pregnancies (spontaneous miscarriage, elective termination, ectopic pregnancy, normal birth, or congenital abnormality) occurring from the first date of the first dose until 90 days after the last dose should, if possible, be followed up and documented.

8.7 REGULATORY REPORTING FOR STUDIES CONDUCTED UNDER CCR-SPONSORED IND

Following notification from the investigator, CCR, the IND sponsor, will report any suspected adverse reaction that is both serious and unexpected. CCR will report an AE as a suspected adverse reaction only if there is evidence to suggest a causal relationship between the study product and the adverse event. CCR will notify FDA and all participating investigators (i.e., all investigators to whom the sponsor is providing drug under its INDs or under any investigator's IND) in an IND safety report of potential serious risks from clinical trials or any other source, as soon as possible, in accordance to 21 CFR Part 312.32.

All serious events will be reported to the FDA at least annually in a summary format.

Version Date: 09/14/2021

9 CLINICAL MONITORING

As a sponsor for clinical trials, FDA regulations require the CCR to maintain a monitoring program. The CCR's program allows for confirmation of: study data, specifically data that could affect the interpretation of primary and secondary study endpoints; adherence to the protocol, regulations, ICH E6 and SOPs; and human subjects protection. This is done through independent verification of study data with source documentation focusing on:

- Informed consent process
- Eligibility confirmation
- Drug administration and accountability
- Adverse events monitoring
- Response assessment.

The monitoring program also extends to multi-site research when the CCR is the coordinating center.

This trial will be monitored by personnel employed by a CCR contractor. Monitors are qualified by training and experience to monitor the progress of clinical trials. Personnel monitoring this study will not be affiliated in any way with the trial conduct.

10 STATISTICAL CONSIDERATIONS

10.1 STATISTICAL HYPOTHESIS

- Primary Endpoints:
 - Maximum tolerated dose (MTD) of rhIL-15 administered intravenously for 5 days in combination with obinutuzumab
 - Frequency (number and percentage) of treatment-emergent AEs
- Secondary Endpoints:
 - o Overall response rate (including CR, CRi, and PR)
 - o Proportion of patients who are MRD-negative
 - o Duration of response (for patients who do and do not achieve MRD-negativity)
 - o Progression-free, event-free, and overall survival

10.2 SAMPLE SIZE DETERMINATION

The MTD will be based on the assessment of DLT during the first cycle of treatment and will be defined as the dose level at which less than one-third of patients (0 of 3 or 0-1/6 patients) treated experience a DLT, with the next higher dose level demonstrating one-third or a greater number of patients ($\geq 2-3$ or $\geq 2-6$ patients) having a DLT. If a subject did not experience a DLT and did not finish one cycle of treatment (28 days) he or she will not be evaluable for determination of the MTD and would be replaced in the dose level. An additional 3 to 6 patients will be enrolled at the MTD, so that a total of 9 patients will be treated at this dose.

Using this dose-escalation scheme the probability of escalating to the next dose level will be based on the true rate of DLT at the current doses given by the following table (each group will be

Version Date: 09/14/2021

considered independently of the other); Thus, if the true underlying proportion of DLTs is 50% at the current dose there is a 17% probability of escalating to the next dose.

True toxicity at a given dose	10%	20%	30%	40%	50%	60%
Probability of escalating	0.91	0.71	0.49	0.31	0.17	0.08

If all three dose levels are evaluated with 6 patients per dose level and 9 total patients at the MTD, a maximum of 21 evaluable patients will be enrolled. To account for non-evaluable patients, accrual ceiling will be set at 24 patients. Similarly, if all dose levels are evaluated with 3 patients per dose level and 9 total patients at the MTD, the minimum number of evaluable patients required will be 12. It is expected that the accrual can be completed in 24 months.

10.3 POPULATIONS FOR ANALYSES

10.3.1 Evaluable for toxicity:

All patients will be evaluable for toxicity from the time of their first treatment with rhIL-15.

10.3.2 Evaluable for objective response:

Only those patients who have measurable disease present at baseline, have received at least one cycle of therapy, and have had their disease re-evaluated will be considered evaluable for response. These patients will have their response classified according to the definitions stated below. (NOTE: Patients who exhibit objective disease progression prior to the end of cycle 1 will also be considered evaluable.)

10.3.3 Evaluable Non-Target Disease Response:

Patients who have lesions present at baseline that are evaluable but do not meet the definitions of measurable disease, have received at least one cycle of therapy, and have had their disease re-evaluated will be considered evaluable for non-target disease. The response assessment is based on the presence, absence, or unequivocal progression of the lesions.

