2 ELIGIBILITY ASSESSMENT AND ENROLLMENT

2.1 ELIGIBILITY CRITERIA

- 2.1.1 Inclusion Criteria
- 2.1.1.1 Patients must have a confirmed diagnosis of chronic lymphocytic leukemia/small lymphocytic lymphoma that expresses CD20 as confirmed by new/fresh peripheral blood sample collection and review by Laboratory of Pathology, NCI
- 2.1.1.2 Measurable or evaluable disease (see Section 6.3)
- 2.1.1.3 Patients must have received prior treatment required as follows: CLL that is refractory or relapsed following therapy with a BTK inhibitor OR have relapsed/refractory CLL and are intolerant of BTK inhibitor therapy; in addition, patients with del(17p) must also be refractory or relapsed after, or intolerant to, therapy with venetoclax; patients who have received prior obinutuzumab are eligible regardless of response to the drug.
- 2.1.1.4 Active disease requiring treatment, as defined by at least one of the following (per IWCLL 2018 consensus criteria):
 - Evidence of progressive marrow failure as manifested by the development of, or worsening of, anemia (Hb <10 g/dL) and/or thrombocytopenia (platelet counts $<100 \times 10^9$ /L).
 - Massive (i.e., ≥6 cm below the left costal margin) or progressive or symptomatic splenomegaly.
 - Massive nodes (i.e., ≥10 cm in longest diameter) or progressive or symptomatic lymphadenopathy.
 - Progressive lymphocytosis with an increase of ≥50% over a 2-month period, or lymphocyte doubling time (LDT) <6 months.
 - Autoimmune complications including anemia or thrombocytopenia poorly responsive to corticosteroids.
 - Symptomatic or functional extranodal involvement (eg, skin, kidney, lung, spine).
 - Disease-related symptoms as defined by any of the following:
 - Unintentional weight loss $\ge 10\%$ within the previous 6 months.
 - Significant fatigue (ie, ECOG performance scale 2 or worse; cannot work or unable to perform usual activities).
 - o Fevers 38.0°C for 2 or more weeks without evidence of infection.
 - Night sweats for ≥ 1 month without evidence of infection.
- 2.1.1.5 ≥18 years of age on day of signing informed consent

NOTE: Because no dosing or adverse event data are currently available on the use of rhIL-15 in combination with obinutuzumab in patients <18 years of age, children are excluded from this study, but will be eligible for future pediatric trials

Version Date: 09/14/2021

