6.3 RESPONSE CRITERIA

Responses for spleen and lymphadenopathy will be assessed using CT scan measurements and not physical exam. Response assessments will be made by IWCLL 2018 guidelines(9). Response includes complete response (CR), and partial response (PR).

	Criteria of response								
Response	CR	PR	PD	SD					
Group A ^A									
Lymphadenopathy ^B	None >1.5cm	Decrease ≥50%	Increase ≥50% or any new lesion > 1.5cm	Change of - 49% to +49%					
Liver and/or spleen size	Spleen size <13cm; liver size normal	Decrease ≥50% (from baseline)	Increase ≥50% from baseline or from response	Change of - 49% to +49%					
Constitutional symptoms	None	Any	Any	Any					
Circulating lymphocyte count	Normal	Decrease ≥50% from baseline	Increase ≥50% over baseline ^D	Change of - 49% to +49%					
Group B ^A									
Platelet count	>100,000/ μL	>100,000/ µL or increase ≥50% over baseline	Decrease ≥50% from baseline secondary to CLL	Change of - 49% to +49%					

Version Date: 09/14/2021

Criteria of response									
Response	CR	PR	PD	SD					
Hemoglobin	>11.0 g/dL (untransfused and without erythropoietin)	>11.0 g/dL or increase ≥50% over baseline	Decrease ≥50% from baseline secondary to CLL	Increased but <11.0 g/dL or <50% over baseline, or decrease <2 g/dL					
Bone marrow ^C	Normocellular, no CLL cells, no B-lymphoid nodules.	Presence of CLL cells, or of B-lymphoid nodules, or not done	Increase of CLL cells by ≥50% on successive biopsies	No change in marrow infiltrate					

Footnotes:

CR (**complete response**): Disease-related constitutional symptoms resolved and all above criteria met, includes bone marrow biopsy

CRi (complete response with incomplete marrow recovery): CR with incomplete hematopoietic recovery **PR (partial response):** Two criteria from Group A if abnormal at baseline plus one of the criteria from Group B must be met, requires the absence of growth factor or transfusion support

SD (stable disease): Defined as not achieving CR, or PR, but not fulfilling the criteria for PD will be considered to have stable disease (which is equivalent to no response)

PD (**progressive disease**): One criteria from Group A or B are met or development of transformation to a more aggressive histology

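### The response-evaluable populations in 10.3.2 and 10.3.3 rest on an undefined term and a lesion-only rule that do not match the IWCLL criteria in 6.3

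*Combined protocol and SAP*

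**What the plan says.** Eligibility criterion 2.1.1.2 asks for "Measurable or evaluable disease (see Section 6.3" and so sends the reader to 6.3 for the meaning. Criterion 2.1.1.4 needs only one sign of active disease. One qualifying sign is "Progressive lymphocytosis with an increase of ≥50% over a 2-month period, or lymphocyte doubling time (LDT) <6 months"; another is progressive marrow failure.

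Section 6.3 states "Response assessments will be made by IWCLL 2018 guidelines(9". Its table has Group A items (nodes, liver/spleen, constitutional symptoms, circulating lymphocyte count) and Group B items (platelets, hemoglobin, marrow). CR needs every criterion, with marrow biopsy. PD needs one criterion from either group, or transformation. For PR, "Two criteria from Group A if abnormal at baseline plus one of the criteria from Group B must be met".

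Section 10.3.2 restricts the response-evaluable set to "Only those patients who have measurable disease present at baseline, have received at least one cycle of therapy, and have had their disease re-evaluated", and also admits patients who progress before the end of cycle 1. It adds: "These patients will have their response classified according to the definitions stated below".

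Section 10.3.3 sets up a second population: "Patients who have lesions present at baseline that are evaluable but do not meet the definitions of measurable disease". For them, "The response assessment is based on the presence, absence, or unequivocal progression of the lesions".

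Section 10.4.3 says that response reports should cover all study patients and include at least a section on all eligible patients. A rate in evaluable patients only may be added, with exclusions explained. Section 10.4.1 promises a response rate with a 95% confidence interval but does not say which rate is the main one.

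**The concern.** The measurable versus non-target split is the language of solid-tumor response assessment. CLL response under 6.3 is a composite of nodes, organs, symptoms, blood counts and marrow. Putting the one on top of the other raises two problems.

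First, the gate into the evaluable set is a term that nobody can look up. Whoever builds the analysis set must decide whether a lymphocyte count is measurable disease, and could do so after seeing outcomes.

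Second, patients routed to 10.3.3 are judged on lesions alone, while 6.3 judges everyone on Groups A and B. The same patient could be progressing under one section and not under the other. Overall response (CR, CRi and PR) is a secondary endpoint, and duration of response and PFS use progression too. With so few patients, a handful of reclassifications would show.

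**Working it through.** **Step 1. Look for the definition.** The pointer from 2.1.1.2 leads to 6.3. That section has a response table with footnotes: new nodal lesions above 1.5 cm, a sum of products over up to 6 nodes, and mention of target lesions in footnote B. It does not define measurable, evaluable or non-target disease. In 10.3.2 the reader is told to look below, but what follows in Section 10 is 10.3.3 and the analysis text, with no response definitions.

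**Step 2. Patient with lymphocytosis only.** Suppose the patient meets 2.1.1.4 by progressive lymphocytosis, has no enlarged node, and enters because the disease is evaluable under 6.3.

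| Section | Result |
|---|---|
| 10.3.2, lesion reading | Not evaluable: no measurable lesion |
| 10.3.2, reading by 6.3 items | Evaluable: the lymphocyte count is scored by percentage change |
| 10.3.3 | Not covered: requires lesions at baseline |
| 6.3 | CR, SD or PD can be assigned; PR is uncertain, because the rule on two Group A criteria is unclear when only one is abnormal |

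So the patient fits neither evaluable population on the first reading and fits 10.3.2 on the second. The text does not settle which applies. The reference in 10.3.3 to lesions that fall short of a definition of measurable disease favors the first.

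**Step 3. Patient with non-measurable nodes.**

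| Course | Under 10.3.3 | Under 6.3 |
|---|---|---|
| Nodes unchanged; lymphocyte count rises enough to meet the table and footnote D (at least 50%, confirmed, CD19 count above 5,000/μL at least once) | Lesions present, no progression | PD: one Group A criterion suffices |
| Nodes disappear; marrow still contains CLL cells | Lesions absent | Not CR: all criteria are required, with biopsy |

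The two rules can therefore disagree in both directions.

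**Step 4. How far the denominator could matter.** The plan's own maximum in 10.2 reproduces: 6 + 6 + 9 = 21 evaluable patients (accrual ceiling 24). The documents give neither an expected response rate nor the share of patients without a measurable lesion, so the following is an assumption: 21 patients, 7 responders under 6.3. If k patients are left out, r of them responders, the evaluable-only rate is (7 − r)/(21 − k). Exact 95% limits for x of n are the 2.5% point of Beta(x, n − x + 1) and the 97.5% point of Beta(x + 1, n − x).

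| Left out (k) | Responders among them (r) | Rate | 95% CI |
|---|---|---|---|
| 0 | 0 | 7/21 = 33.3% | 14.6–57.0 |
| 3 | 0 | 7/18 = 38.9% | 17.3–64.3 |
| 3 | 1 | 6/18 = 33.3% | 13.3–59.0 |
| 3 | 3 | 4/18 = 22.2% | 6.4–47.6 |
| 6 | 0 | 7/15 = 46.7% | 21.3–73.4 |
| 6 | 2 | 5/15 = 33.3% | 11.8–61.6 |
| 6 | 6 | 1/15 = 6.7% | 0.2–31.9 |

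The rate can rise, fall or stay put. The rows with all or none responding are extremes.

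**The case against.** The best answer is 10.4.3. It makes the all-eligible rate mandatory and the evaluable-only rate an extra, and it demands reasons for exclusions. A reader might infer from 10.3.2 that patients with blood or marrow disease only are dropped from the trial's response result. The documents do not support that: such patients stay in the required rate and can leave only the optional one. Even that exclusion is an inference, since 10.3.2 speaks of disease and not of lesions, and the only pointer leads to a table that includes the lymphocyte count. All of this stands.

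Two further limits also stand. Section 10.3.3 covers only lesions that are evaluable but not measurable, so a patient with measurable nodes and nothing else remains under 10.3.2. And 6.3 is not free of lesion terms.

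It can also be said that 10.3.3 names no CR, PR, SD or PD category and that 6.3 claims all response assessments, so there is only one classification. This stands in part. Section 10.3.3 still states the basis of response assessment for its own population, and nothing says that 6.3 overrides it. Section 10.4.3 fixes the denominator; it does not say which rule classifies these patients within it.

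**Conclusion.** The point holds as an inconsistency between 10.3 and 6.3. Three things are established: *measurable disease* has no definition, the reference to definitions below leads nowhere in Section 10, and the 10.3.3 rule can contradict 6.3. Whether patients with blood or marrow disease only fall outside both evaluable populations is conditional on the lesion reading.

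The reach is limited to a secondary endpoint that is estimated without a hypothesis. The exclusion can affect only the optional evaluable-only rate. The classification conflict can also reach the all-eligible rate and, if the 10.3.3 rule were used to call progression, duration of response and PFS. The MTD and the sample size do not depend on any of this.

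A reader might also infer a bias in a known direction, for instance that the evaluable rate understates activity because the treatment acts on circulating cells. The documents give no response rate by disease site and no share of such patients, so neither size nor direction can be derived. The figures above show sensitivity under an assumed 7 of 21 and are not predictions.

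**What to change.** - In 10.3.2, replace the measurable-disease condition with *at least one CLL-related Group A or B item of Section 6.3 abnormal at baseline*. Keep the one-cycle, re-evaluation and early-progression conditions.
- In 10.3.2, replace the reference to definitions below with a reference to Section 6.3.
- Delete 10.3.3, so that every patient is classified by 6.3.
- In 10.4.3, name the all-eligible rate as the main response analysis and the evaluable-only rate as supportive.
- Leave eligibility criterion 2.1.1.2 as it is, apart from reconciling its pointer to 6.3. Active CLL is already required by 2.1.1.4, so no eligibility rewrite is needed.

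These changes do not settle how the PR rule in 6.3 applies when fewer than two Group A items are abnormal at baseline; that needs its own clarification.

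Cost: wording only, through the IRB review that any amendment requires. No new data, visits or patients.
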